#### **4.6.7 Concomitant Medications**

The original terms recorded on the patients' eCRF by the Investigator for concomitant medications will be standardized by the Sponsor by assigning preferred terms.

Concomitant medications will be presented in summary tables and listings.

#### **4.6.8 Exposure to Study Medication**

The following extent to study medication will be summarized by treatment arm:

- Duration of treatment, to be calculated as first day to last day to masked study medication
- Relative extent of exposure as number of given intravitreal injections divided by number of planned intravitreal injections of masked study medication during the treatment duration of a patient.

#### **4.7 MISSING DATA**

An analysis of the sensitivity of the assumptions on missing values may be performed for the primary efficacy variable.

The primary endpoint analysis using the MMRM assumes a missing at random (MAR) missing-data mechanism (i.e., the probability that missing data are dependent on other observed variables, but not on the missing data itself.)

A LOCF imputation will be applied to the primary end-point as a sensitivity analysis.

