4.7.1.1 Discontinuation from Study Drug

Patients must discontinue study treatment if they experience any of the following:

- Pregnancy
- Drop in BCVA by ≥ 30 letters if considered to be adverse and related to study treatment in the study eye (*compared with the last assessment of visual acuity prior to the most recent treatment*) and lasting for more than 1 hour
- Endophthalmitis in the study eye
- Severe intraocular inflammation (*i.e., 4+anterior chamber cell/flare or 4+tritis; see the definition of intraocular inflammation in Section 5.3.5 and grading scales for assessment in Appendix 3*)
- Retinal detachment in the study eye
- Vitreous hemorrhage that will preclude examination of macula and retinal imaging in the study eye
- Surgical intervention (*i.e., conventional surgery, vitreous tap, or biopsy with IVT injection of anti-infectives or laser or retinal cryopexy with gas*) to prevent permanent loss of sight

Patients who discontinue study treatment prematurely will be asked to return to the clinic for an early termination visit (see Section 4.6.6.3) and may undergo assessments as outlined in the SoA. The primary reason for premature study treatment discontinuation should be documented on the appropriate eCRF.

Every effort should be made to obtain information on patients who withdraw from the study. The primary reason for withdrawal from the study should be documented on the appropriate eCRF.

Patients will not be followed up as part of the study for any reason after consent has been withdrawn.

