### **2.3 DETERMINATION OF SAMPLE SIZE**

#### **2.3.1 Sample Size and Power for Treatment-Naive Population Evaluation**

The sample size for the treatment-naive population is based on the primary efficacy outcome of mean change in BCVA from baseline to Week 36. Each RO6867461 dose or dose regimen group (Arms B, C, and D) will be compared to the control group (Arm A).

Consider 68 patients randomized to Arm A and 45 randomized to each of Arms B, C, and D, with a drop-out rate of 10%. Assuming a standard deviation of 13.5 letters, this sample size would provide approximately 80% power to detect a true difference of 5.9 letters at the one-sided  $\alpha$  level of 10%. The minimum detectable difference would be approximately 3.5 letters.

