#### **4.5.4 Sensitivity Analyses**

Effects of prognostic factors on the BCVA change from baseline will be investigated using the MMRM model described in section 4.5.1. The measurement at BL (baseline) of each of the following variables may be used as covariates in the model:

- Age
- CNV component area, (FFAArea)
- LLD (Difference between BCVATOT for the BCVA assessment and LLVATOT for the LLVA assessment)

The sensitivity analyses will be performed separately for each covariate in populations A and C.

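### LOCF is the only missing-data sensitivity analysis the SAP commits to, and it cannot show how far missing-at-random must fail before a primary conclusion changes

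*SAP*

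**What the plan says.** SAP 4.7 makes three statements.

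- The assumption: "The primary endpoint analysis using the MMRM assumes a missing at random (MAR) missing-data mechanism".
- The commitment: "A LOCF imputation will be applied to the primary end-point as a sensitivity analysis".
- An option: "An analysis of the sensitivity of the assumptions on missing values may be performed for the primary efficacy variable". No method, size of departure, reference arm or trigger is given.

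No other section fills the gap. SAP 4.5.4, although headed as sensitivity analyses, concerns covariates: "Effects of prognostic factors on the BCVA change from baseline will be investigated using the MMRM model described in section 4.5.1", with age, CNV component area and low-luminance deficit as candidates. The Mann-Whitney fallback in SAP 4.5.1.1 answers non-normality. Protocol 6.6 names no missing-data sensitivity analysis.

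On how data go missing, Protocol 4.7.1 lists worsening disease among the reasons for stopping treatment or leaving the study. Protocol 4.7.1.1 lists mandatory treatment stops, among them endophthalmitis, retinal detachment, a treatment-related loss of 30 letters or more, and "Severe intraocular inflammation". Patients who stop are asked back for an early termination visit. Protocol 4.6.6.3 places it 28 (+7) days after the last treatment for those who have not withdrawn consent, and Appendix 1 schedules BCVA there. Standard-of-care treatment may follow that visit. Continued visits to Week 36 are not described.

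On decisions, SAP 4.5.1.1 declares significance for Arm B, C or D versus A at an unadjusted two-sided p below 0.2. SAP 4.5.1.2 states no such rule for Arm E versus A in Population C.

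**The concern.** A sensitivity analysis for an MMRM should ask how the answer changes as MAR is relaxed. LOCF does not ask that. It fixes every missing Week 36 value at the last observation and treats the filled-in value as if it had been measured. It has no parameter for how much worse the missing patients might be.

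Both the MMRM and LOCF are computed from recorded values only. If patients deteriorate after their last recorded BCVA by more than their earlier values predict, neither estimate moves. The gap between the two therefore carries no information about that deterioration: they can agree when MAR is false and differ when it is true.

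At stake is the robustness statement attached to the two primary comparisons. It matters most for a result close to the significance threshold, or where drop-out is higher than planned or unequal between arms.

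**Working it through.** **Inputs.** Treatment-naive comparison (SAP 2.3.1): 68 patients in Arm A, 45 in each of Arms B, C and D, 10% drop-out; "Assuming a standard deviation of 13.5 letters"; "approximately 80% power to detect a true difference of 5.9 letters at the one-sided" 10% level; minimum detectable difference about 3.5 letters. Incomplete-responder comparison (SAP 2.3.2): 68 per arm, 65% in the subgroup, 10% drop-out, SD 9.7, difference 4.7, one-sided 10%. The deltas below are assumptions, because the documents give none.

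**1. The plan's own figures.** Completers are 68 × 0.9 = 61.2 and 45 × 0.9 = 40.5.

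- SE = 13.5 × √(1/61.2 + 1/40.5) = 2.73 letters.
- Threshold = 1.2816 × 2.73 = 3.5 letters, as stated.
- Power at 5.9 letters = Φ(5.9/2.73 − 1.2816) = 81%, against a stated figure of about 80%. The two-sided 0.2 rule gives the same power.

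**2. Effect of a departure from MAR.** Let p be the drop-out fraction and delta the letters by which drop-outs fall below their MAR prediction.

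Shift in the difference = p(test) × delta(test) − p(A) × delta(A).

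With 10% in each arm and a departure in the test arm only, delta = 10 gives 0.10 × 10 = 1.0 letter. Equal deltas at equal drop-out cancel. With 15% versus 5% drop-out and delta = 10 in both arms, the shift is 1.5 − 0.5 = 1.0 letter.

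**3. Tipping points, test arm only.** Tipping delta = (observed difference − threshold)/p, with the SE held at its completer-based value.

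| Comparison | Observed difference | Drop-out | Tipping delta |
|---|---|---|---|
| B, C or D vs A | 5.9 | 10% | (5.9 − 3.5)/0.10 ≈ 24 |
| B, C or D vs A | 4.5 | 10% | (4.5 − 3.5)/0.10 ≈ 10 |
| B, C or D vs A | 5.9 | 15% | ≈ 15 |
| B, C or D vs A | 5.9 | 20% | ≈ 11 |
| E vs A, incomplete responders | 4.7 | 10% | (4.7 − 2.79)/0.10 ≈ 19 |

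For 15% and 20% drop-out the SE is recomputed with fewer completers. In the last row, completers are 68 × 0.65 × 0.9 = 39.8 per arm, SE = 9.7 × √(2/39.8) = 2.17 and threshold = 1.2816 × 2.17 = 2.79 letters.

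**4. LOCF beside the MAR estimate.** A large-sample simulation illustrates the reasoning. Its settings are not in the documents: a control gain of 8 letters, an early plateau, strongly correlated visits, 10% drop-out per arm, and drop-out unrelated to observed values.

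| Test-arm drop-outs | True difference | MAR estimate | LOCF |
|---|---|---|---|
| As MAR predicts | 5.88 | 5.88 | 5.80 |
| 15 letters worse | 4.40 | 5.89 | 5.81 |

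The closeness of LOCF to the MAR estimate depends on those settings. That neither moves with the departure does not.

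**The case against.** The strongest reply has four parts.

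*The plan already allows the analysis.* A reader might infer that the SAP ignores departures from MAR. It does not: SAP 4.7 opens with the optional analysis of exactly this. Nor does the SAP claim that LOCF tests MAR, and no analysis can test it. This stands. What remains is that the option is unnamed and uncommitted, so it could be chosen, or skipped, after the data are seen.

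*The mandated stops are largely observed.* A reader might infer that endophthalmitis or a 30-letter loss vanishes from the analysis. The documents do not support that. A 30-letter loss is itself a recorded BCVA, early termination includes BCVA, and SAP 4.4.1 assigns off-schedule assessments to the nearest target visit. Drop-out that depends on recorded vision is compatible with MAR, and both methods use the poor value. LOCF may even be harsher: for a patient 30 letters below expectation, with an assumed visit correlation of 0.6 to 0.8 and equal variances, it carries forward 30 × (1 − 0.8) = 6 to 30 × (1 − 0.6) = 12 letters more loss than the model would predict. This also stands. It confines the gap to what happens after the last recorded BCVA and to patients with no BCVA after the event.

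*Population C.* A reader might infer that LOCF gives zero change to anyone who leaves soon after Week 12. The SAP does not say that Week 12 may be carried forward, and a patient dosed at Week 12 who attends early termination has a BCVA at about Week 16. The SAP is silent here; it does not set a zero.

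*Scale and purpose.* SAP 4.8 calls the study hypothesis-generating, and 24 letters is about 1.8 times the assumed SD (24/13.5). This limits the priority. It does not make LOCF informative about departures from MAR.

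**Conclusion.** The point holds as a modest one. The SAP declares MAR, commits only to LOCF, and leaves without a method the analysis that would show how far MAR must fail before a conclusion changes.

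At the planned drop-out, a result at the design difference of 5.9 letters is hard to overturn: it needs a departure of about 24 letters confined to test-arm drop-outs. A result of 4.5 letters, which would be declared significant at the planned SE, needs about 10. The stronger reading, that the primary conclusions are fragile in general, is not supported by these figures.

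The figures rest on 10% drop-out in each arm, the planned SDs, an unchanged SE, and no departure in Arm A. For Population C they also assume the planned 65% and a full 10% missing at Week 36. SAP 4.4.2 excludes patients without a Week 12 value, so if the 10% includes earlier leavers, the missing fraction is smaller and the tipping delta larger.

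**What to change.** Replace the optional sentence in SAP 4.7 with a commitment along these lines:

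- For both primary comparisons, run multiple imputation under MAR, followed by a delta adjustment of missing Week 36 BCVA in the RO6867461 arms over a pre-stated grid, for example 0, 5, 10, 15 and 20 letters and onward until the conclusion changes. Optionally vary the Arm A delta as well, since equal departures at equal drop-out cancel.
- For Arms B, C and D versus A, report the delta at which the two-sided p crosses 0.2.
- For Arm E versus A in Population C, report the estimate and confidence interval across deltas, and the delta at which the one-sided 10% level of its sample-size calculation is crossed. The 0.2 rule should not be assumed to apply there, because the SAP does not state it.
- Keep LOCF as supportive if wanted, stating which model it feeds and whether the Week 12 value may be carried forward in Population C. Removing it is not necessary.

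The cost is SAP wording and one imputation program. Conduct, sample size and the primary model are untouched. The downside is that the robustness statement may turn out less favourable.

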#### **4.8 INTERIM ANALYSES**

Given the hypothesis-generating nature of this study, the Sponsor may conduct up to two additional interim analyses of efficacy. The decision to conduct such an interim analysis and its timing will be documented in the Sponsor's study master file prior to the conduct of the interim analysis. The Clinical Study Report will also document that such an interim analysis occurred. The interim analysis, should it occur, will be performed and interpreted by members of the IMC and DRC who would then be unmasked at the treatment group level. Access to treatment assignment information will follow the Sponsor's standard procedures.

Details of the interim analyses are described in the IMC charter.

## Appendix 1

### SYNOPSIS OF PROTOCOL NUMBER BP29647

TITLE	A MULTIPLE-CENTER, MULTIPLE-DOSE AND REGIMEN, RANDOMIZED, ACTIVE COMPARATOR CONTROLLED, DOUBLE-MASKED, PARALLEL GROUP, 36-WEEK STUDY TO INVESTIGATE THE SAFETY, TOLERABILITY, PHARMACOKINETICS, AND EFFICACY OF RO6867461 ADMINISTERED INTRAVITREALLY IN PATIENTS WITH CHOROIDAL NEOVASCULARIZATION SECONDARY TO AGE-RELATED MACULAR DEGENERATION
PROTOCOL NUMBER:	BP29647
VERSION:	3
EUDRACT NUMBER:	N/A
IND NUMBER:	119225
TEST PRODUCT:	RO6867461
PHASE:	II
INDICATION:	Choroidal neovascularization (CNV) secondary to age-related macular degeneration (AMD)
SPONSOR:	F. Hoffmann-La Roche Ltd.

#### **OBJECTIVES**

##### **Primary:**

The primary objective of this study is as follows:

- To evaluate the efficacy of RO6867461 compared to ranibizumab monotherapy in treatment-naïve and anti-vascular endothelial growth factor (VEGF)-incomplete-responder patients with CNV secondary to AMD.

##### **Secondary:**

The secondary objectives of this study are as follows:

- To assess the safety of multiple intravitreal (IVT) doses of RO6867461
- To assess systemic pharmacokinetics of RO6867461
- To investigate pharmacodynamics (PD) and anatomical outcomes informing on the mechanism of action of RO6867461
- To investigate the formation of plasma anti-RO6867461 antibodies
- To investigate 2 different RO6867461 dosing regimens

##### **Exploratory:**

The exploratory objectives of this study are as follows:

- To evaluate RO6867461 effects on plasma levels of markers of angiogenesis and inflammation
- To investigate RO6867461 concentration and, if sample volume allows, inflammatory and pro-angiogenic factors, in aqueous humor samples (optional) and vitreous (optional)
- To evaluate the effect of genetic polymorphisms in genes associated with AMD and/or involved in angiogenesis and response to RO6867461

---

## **STUDY DESIGN**

### **Description of Study**

Multiple-center, multiple-dose and regimen, randomized, active comparator controlled, double-masked, five parallel group, 36-week study in patients with CNV secondary to AMD. The five groups of this study are as follows:

- Arm A: 0.5 mg ranibizumab IVT every 4 weeks for 32 weeks (9 injections)
- Arm B: 1.5 mg RO6867461 IVT every 4 weeks for 32 weeks (9 injections)
- Arm C: 6 mg RO6867461 IVT every 4 weeks for 32 weeks (9 injections)
- Arm D: 6 mg RO6867461 IVT every 4 weeks up to Week 12 (4 injections), followed by 6 mg RO6867461 IVT every 8 weeks (i.e., on Weeks 20 and 28; 2 injections)
- Arm E: 0.5 mg ranibizumab IVT every 4 weeks up to Week 8 (3 injections), followed by 6 mg RO6867461 IVT every 4 weeks (6 injections)

The study will allow evaluation of RO6867461 in a treatment-naïve patient population (comparison of Arms A, B, C, and D) and an anti-VEGF–incomplete-responder patient population that meets a predefined criterion at Week 12 (comparison between Arms A and E). Only one eye will be chosen as the study eye.

---

### **NUMBER OF PATIENTS**

In the initial recruitment period, up to 271 patients with CNV secondary to AMD are expected to be enrolled in the study. Up to 45 (Arms B, C, and D) or 68 (Arms A and E) patients are expected to be randomized per arm of the study (3:2:2:2:3 randomization scheme).

An interim analysis might be conducted to adapt the recruitment up to a maximum of 343 patients in order to have approximately 80 patients in the anti-VEGF–incomplete-responder subgroup completing the study.

---

### **TARGET POPULATION**

Male and female patients of  $\geq 50$  years of age with treatment-naïve CNV secondary to AMD.

---

### **INCLUSION/EXCLUSION CRITERIA**

#### **Inclusion Criteria:**

Patients must meet the following criteria at study entry:

#### ***Ocular criteria for study eye:***

- Treatment-naïve with CNV secondary to AMD, with subfoveal CNV or juxtafoveal CNV with a subfoveal component related to the CNV activity by *fundus fluorescein angiography* (FFA) or *spectral domain optical coherence tomography* (SD-OCT) (such as subretinal fluid, subretinal hyper-reflective material, evidence of leakage, or hemorrhage)
- Best corrected visual acuity (BCVA) letter score of 73 to 24 letters (inclusive) on Early Treatment Diabetic Retinopathy Study (ETDRS)-like charts (20/40 to 20/320 Snellen equivalent) on Day 1. Proportion of patients with BCVA letter score of 73 to 69 letters inclusive (20/40 Snellen equivalent) on Day 1 will be limited to a maximum of 40% of the planned sample size
- CNV lesion of all types (predominantly classic, minimally classic, or occult) with:
  - Total lesion size (including blood, atrophy, fibrosis, and neovascularization) of  $\leq 6$  disc areas (DAs) by FFA
  - CNV component area of  $\geq 50\%$  of total lesion size by FFA
  - Active CNV confirmed by FFA (evidence of leakage)
  - CNV exudation confirmed by SD-OCT (presence of fluid)
- Clear ocular media and adequate pupillary dilatation to allow acquisition of good quality retinal images to confirm diagnosis

#### ***General Criteria:***

---

RO6867461—F. Hoffmann-La Roche Ltd  
Statistical Analysis Plan BP29647

- 
- Able and willing to provide written informed consent and to comply with the study protocol according to International Conference on Harmonization (ICH) and local regulations. Alternatively, a legally authorized representative must be able to consent for the patient according to the ICH and local regulations
  - Age  $\geq 50$  years
  - For women who are not postmenopausal (i.e.,  $\geq 12$  months of non-therapy-induced amenorrhea or surgically sterile (absence of ovaries and/or uterus) agreement to remain abstinent or use combined contraceptive methods that result in a failure rate of  $< 1\%$  per year during the treatment period and at least through Week 36.
    - Examples of contraceptive methods with an expected failure rate of  $< 1\%$  per year include male sterilization, hormonal implants, proper use of combined oral or injected hormonal contraceptives, and certain intrauterine devices. Alternatively, two methods (e.g., two barrier methods such as a condom and a cervical cap) may be combined to achieve a failure rate of  $< 1\%$  per year, barrier methods must always be supplemented with the use of a spermicide.
  - Males must agree to use a barrier method of contraception starting from first treatment administration for at least 2 months post-last treatment administration.
  - Patients must be willing not to participate in any other clinical trial including an investigational medicinal product (IMP) or device up to completion of the current study.

**Exclusion Criteria:**

Patients who meet any of the following criteria will be excluded from study entry:

**Ocular criteria for study eye:**

- CNV due to causes other than AMD, such as ocular histoplasmosis, trauma, pathological myopia, angioid streaks, choroidal rupture, or uveitis
- Central serous chorioretinopathy (CSC) at screening
- Retinal pigment epithelial tear involving the macula
- On FFA
  - Subretinal hemorrhage of  $> 50\%$  of the total lesion area and/or that involves the fovea
  - Fibrosis or atrophy of  $> 50\%$  of the total lesion area and/or that involves the fovea
- Any prior or concomitant treatment for CNV including (but not restricted to) IVT treatment (steroids, anti-VEGF, transplasminogen activator, ocriplasmin,  $C_3F_8$  gas, air), periorbital pharmacological intervention, argon LASER photocoagulation, verteporfin photodynamic therapy, diode laser, transpupillary thermotherapy, or surgical intervention
- Cataract surgery within 3 months of baseline assessments
- Any other intraocular surgery (pars plana vitrectomy, glaucoma surgery, corneal transplant, radiotherapy)
- Prior IVT treatment (including anti-VEGF medication) except for management of cataract complication with steroid IVT treatment
- Prior periocular pharmacological intervention for other retinal diseases

**Concurrent Ocular Conditions:**

- Any concurrent intraocular condition *in the study eye* (e.g., amblyopia, aphakia, retinal detachment, cataract, diabetic retinopathy or maculopathy, or epiretinal membrane with traction, etc.) that, in the opinion of the Investigator, could either reduce the potential for visual improvement or require medical or surgical intervention
  - Active intraocular inflammation (grade trace or above) *in the study eye*
  - Current vitreous hemorrhage *in the study eye*
  - Uncontrolled glaucoma (e.g., progressive loss of visual fields or defined as intraocular pressure [IOP]  $\geq 25$  mmHg despite treatment with anti-glaucoma medication) *in the study eye*
- 
- Spherical equivalent of refractive error demonstrating more than 8 diopters of myopia *in*

---

*the study eye*

- History of idiopathic or autoimmune-associated uveitis *in either eye*
- Active infectious conjunctivitis, keratitis, scleritis, or endophthalmitis *in either eye*

**Characteristics for fellow eye:**

- Any anti-VEGF treatment within 7 days prior to Day 1
- Any retinal condition that, in the opinion of the Investigator, might require anti-VEGF treatment within 7 days from Day 1

**General Criteria:**

- Any major illness or major surgical procedure within one month before screening
  - Patients with glycosylated hemoglobin HbA1C > 7.5%
  - Uncontrolled blood pressure ([BP] defined as systolic > 180 mmHg and/or diastolic BP > 100 mmHg while patient at rest). If a patient's initial reading exceeds these values, a second reading may be taken *either 30 or more minutes later on the same day, or on another day during the screening period*. If the patient's BP is controlled by antihypertensive medication, the patient should be taking *the same* medication continuously for at least 30 days prior to Day 1
  - Stroke within 12 months prior to Day 1
  - History of other disease, metabolic dysfunction, physical examination finding, or clinical laboratory findings giving reasonable suspicion of a condition that contraindicated the use of the investigational drug or that might affect interpretation of the results of the study or renders the patient at high risk for treatment complications in the opinion of the Investigator
  - For females of childbearing potential, a positive blood pregnancy test
  - Lactating women
  - Known hypersensitivity to ranibizumab, fluorescein, indocyanine green, any ingredients of the formulation used, dilating eye drops, or any of the anesthetic and antimicrobial drops used
  - Any other restriction accorded to the use of
  - Any treatment with an IMP in the 3 months prior to Day 1
- 

